Overview: Design and Methods. This three-year development project consists of 3 stages. **Stage one** (months 1-6) involves establishing a Development Team (DT) that will review the initial draft of TAPES and provide feedback to ensure that TAPES is acceptable to teachers and feasible for the school setting. **Stage two** (months 7-20) involves two successive open trials of the TAPES protocol with 15 teachers and 20 children. This stage will allow for "trial runs" of the training to assess feasibility, acceptability and utility of the training. Data and qualitative feedback gleaned during the first open trial will inform modifications for the second open trial. We will present and discuss data with the DT after each open trial. We will also ask 5 teachers from open trial 1 to test out the revisions for open trial 2. Based on knowledge gained in this stage, appropriate modifications will be made for stage three. **Stage three** (months 21-34) involves a pilot RCT using a randomized controlled design comparing TAPES to the Teacher Anxiety Training (TAT). TAT (developed by the PIs for use in other studies and described below) will be used to represent "typical" teacher professional development training. The RCT will be conducted in three phases. Phase 1 consists of recruiting, randomizing, and training

teachers in either TAPES or TAT. Also during this phase (but after the training), teachers will recruit anxious children and study staff will screen and evaluate them to determine eligibility. In Phase 2 teachers will implement TAPES or TAT. Phase 3 involves a post-intervention (after 8 weeks) and a three-month follow-up assessment of the primary (teacher behavior) and secondary (child) outcomes. Trained independent evaluators (IEs) will assess primary outcomes (teacher behavior). The culmination of these iterative stages will be a final version of the training that will be ready for evaluation in a larger efficacy trial.

DETAILED DESCRIPTION OF EACH STAGE

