
Phase 1 - Recruitment, Randomization, Training, Student Screening, and Baseline

Evaluations: In Phase 1, teachers will be randomly selected from the pool of interested participants and randomized to TAPES or TAT. Once randomized, teachers will complete their assigned training. Teachers will then identify potentially eligible students from their classes and provide information about the study to their parents. Interested parents will contact study staff and complete a brief phone screen. Students who appear eligible based on the phone screen (e.g.,

have elevated anxiety; are in elementary school) will be invited to complete informed consent and a full baseline evaluation with an IE (see Table 1 for measures). Families who "pass" the baseline evaluation (i.e., student obtains a *t* score of 60 on Spence Children's Anxiety Scale (SCAS) and/or a CSR of at least 3 on the ADIS-V) will be considered eligible (see Inclusion/Exclusion criteria below).

Phase 2 – TAPES/TAT Implementation: Teachers will implement TAPES or TAT depending on their random assignment over 8 weeks from child enrollment.

Phase 3 - Post- and Follow-up Evaluations: At the end of the 8 weeks, teachers and children in both groups will complete a post evaluation (see Table of Measures). Teachers, students, and parents will complete a TAPES satisfaction measure and provide feedback to enhance the protocol. Teachers will complete an exit interview. Students who need mental health services will be referred to the school counselor or community provider for treatment. A 3 month follow-up evaluation to assess sustained use of TAPES/TAT skills will be conducted.

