Child Participants. A total of 80 students will participate (20 in the open trials and 60 in the RCT). Within the participating CT districts there are 26 elementary schools and 6,000 students. The student body within CT is diverse in terms of gender, socioeconomic status, and racial/ethnic background (12.3% African American, 22.1% Hispanic/Latino, 57.3% Caucasian, 4.8% Asian, 2.5% two or more Races; 32.9% receive free/reduced priced meals). Children of all races/ethnicities may be eligible to participate and will depend on who volunteers. Child Inclusion/Exclusion Criteria. Inclusion/exclusion criteria for open trials and the pilot RCT were crafted to maximize the generalizability of findings. Because the *primary* aim of this study

were crafted to maximize the generalizability of findings. Because the *primary* aim of this study is to evaluate changes in teacher behavior, and because children whose teacher is randomly assigned to TAT may not receive any evidenced-based assistance, children identified as needing treatment based on the diagnostic interview (regardless of group) will be referred for services. Students receiving services will also be enrolled; all service use will be documented over the course of the study. This approach mimics what naturally occurs in the classroom—that is teachers frequently work with students who may be in outpatient or school-based treatment. Inclusion Criteria: All children must: 1) attend a CT elementary school (i.e., ages 5-12 inclusively); and 2) have elevated anxiety symptoms (i.e., a total SCAS *t* score \geq 60 based on parent and/or child report and/or a clinician severity rating [CSR] of 3 or greater on the ADIS) Students will be excluded if they: 1) have a medical or psychiatric condition contraindicating the study participation (based on clinical interview such as recent suicidality). Ambiguous cases will be decided by the PIs and the school teacher.

Child Recruitment. Teachers will identify potentially eligible youth from their classroom, describe the study to their parents and provide them with study contact information. Parents will

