internal consistency reported at .89 for the total parent anxiety score and .92 for the total child score (Muris, Schmidt, & Merckelbach, 2000; Nauta et al., 2004; Spence, Barrett, & Turner, 2003; Spence, 1998). This measure was selected to facilitate comparisons with published schoolbased studies using the FRIENDS program (Barrett et al., 2005, 2006; Barrett & Turner, 2001). - *Strength and Difficulties Questionnaire- Teacher version* (SDQ; Goodman, 1997) is a 25-item, widely used questionnaire about children's classroom behavior. The teacher-report version has sound psychometric properties (Stone et al., 2010).

-*Teacher Observation of Classroom Adaption-Checklist, Concentration Problems scale* (TOCA-C; Koth, Bradshaw, & Leaf, 2009; Leaf, Schultz, Keys, & Ialongo, 2002) is a measure of student behavioral adjustment that demonstrates high internal consistency and construct validity. The 7-item Concentration Problems scale will be used to assess inattentive behaviors in the classroom. -*Avoidance Hierarchy* – is a measure of the student's top three most frequently avoided behaviors at home and at school, which are assigned by the independent evaluator at baseline. Each behavior is rated on a 7 point Likert scale to assess how often the student avoids engaging in the behavior (1 = never avoid to 7 = avoid every time).

Additional Study Measures:

- *Demographics Form*- This questionnaire assesses child/family information such as child age, family income, parental education, race/ethnicity, etc.

- *Service Utilization Form* is administered at each assessment to document involvement or changes in psychological/psychiatric services. The service utilization form will be modified to include more details related to the sub study including an emphasis on school-based services (including teachers time).

- *Parent Health Questionnaire (PHQ)* will be used to assess parent and teacher anxiety and mood symptoms. This form was adapted from two screening measures (GAD-7 and PHQ-9), which have shown good reliability and validity in primary care settings (Kroenke, Spitzer, & Williams, 2001; Spitzer, Kroenke, Williams, & Löwe, 2006).

Sub Study Measures:

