burnout, teacher efficacy; teacher behavior) and child characteristics (e.g., gender, age, baseline anxiety symptoms, classroom functioning). To test the main hypothesis, that teachers in TAPES, compared to TAT, will have higher knowledge about anxiety reduction, we will examine scores on the *Teacher Knowledge Assessment* at post-training, and at the end of school year as outcomes in GLM controlling for teacher pre-training score. Let y_i denote the post-training or end of school year test score of teacher i, x_{i1} and x_{i2} denote teacher i's group assignment and pre-training test score, respectively, and ε_i denote resident term. Rejecting $\beta_1 \leq 0$ and $\beta_3 \leq 0$ in the model: $y_i = \beta_0 + \beta_1 \times x_{i1} + \beta_2 \times x_{i2} + \beta_3 \times x_{i1} \times x_{i2} + \varepsilon_i$ suggests that TAPES teachers' post-training test scores are higher and they have a greater gain in knowledge than TAT teachers. Teacher-specific covariates can be added to the above model as needed. To test the hypothesis that TAPES, compared to TAT, will result in greater use of anxiety reduction skills in the classroom, IE's Classroom Observation of Teachers Skills rating for each pair of teacher and anxious student at baseline, post-intervention, and 3-month follow-up will be modeled in GLMM. Now rating, y_{ijk} are nested within teacher k and student j, who is nested within teacher k, in the multilevel equations: Level 1: $y_{ijk} = \pi_{0jk} + \pi_{1jk} \times \text{timepoint}_{ijk} + e_{ijk}$; Level 2: $\pi_{0jk} = \beta_{00k} + r_{0jk}$ and $\pi_{1jk} = \beta_{10k} + r_{1jk}$; Level 3: $\beta_{00k} = \gamma_{000} + \gamma_{001} \times w_k + u_{00k}$ and $\beta_{10k} = \gamma_{100} + \gamma_{101} \times w_k + u_{10k}$; where w_k denotes teacher k's intervention-training group assignment with e, r, and u representing error terms in the respective levels. Teacher-specific (e.g., years of teaching experience, teaching efficacy) and child-specific (e.g., age, baseline anxiety severity) covariates can be added to Levels 2 and 3 equations as needed. Aim #4 (Secondary Outcomes): To examine the impact of TAPES relative to TAT on student outcomes. Change scores on student mental health (e.g., Spence Children's Anxiety Scale, SCAS) and academic achievement (e.g., Woodcock-Johnson Tests of Achievement) from pre-to postintervention and 3-month follow-up will be modeled as GLMM similar to above in Aim 3. **Exploratory aims**: To examine mediators (proposed in the theory of change, see Figure 1 in Appendix) and predictors and moderators (e.g. Teacher Background Form, MBI-Educators Scale) of TAPES impact on teacher knowledge and behavior. Structural equation modeling (SEM) will be used to explore potential predictors (e.g., baseline teacher burnout as measured by MBI-ES), mediators (e.g., subscale scores from the OSTES) and moderators (e.g., years of teacher experience) on teacher behavior change (e.g., change score on the Classroom Observation of Teachers Skills at pre-, post-intervention and 3-month follow-up). Sub study: Aim #1: Assess the direct and indirect cost of pediatric anxiety among youth enrolled in the TAPES intervention. This aim involves the modification of existing measures of direct and indirect cost. These measures will be administered to parents and teachers at existing TAPES assessment time points (i.e. baseline, post intervention and three-month follow up). Aim #1a: Estimating the cost of pediatric anxiety through direct and indirect costs. Aim #2: To examine the child and parent benefit of TAPES compared to UC. This aim involves estimating the cost of TAPES relative to the UC condition in relation to direct and indirect costs. Exploratory Aim: To examine family demographic factors as moderators of pediatric anxiety cost. **Power Analysis.** Although this is a development study proposing a small pilot RCT, attempts were made to estimate statistical power for the key outcomes based on existing literatures on similar measures (see White et al., 2011 for Teacher Knowledge Assessment and Barrett et al., 2005 for child anxiety using the SCAS). Using Optimal Design version 3.0 calculations for both variables were based on an anticipated enrollment of 20 teachers in each group (and 1-2 students per teacher). We assumed a conservative within-teacher ICC of 0.10 (Eldridge et al., 2004) and

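### Aim #4 carries over a one-slope time model to the student outcomes without naming the treatment contrast; visit should be a category, with the post and 3-month contrasts reported separately

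*Combined protocol and SAP*

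**What the plan says.** All references are to the combined protocol and SAP.

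- **Model.** Under Aim #3 in the Data Analytic Plan, Level 1 has an intercept and one coefficient on timepoint. Both have student-level and teacher-level error terms. Training group enters at Level 3, on the intercept (γ001) and on the time coefficient (γ101). The plan does not say whether timepoint is numeric or how it is coded.
- **Student outcomes.** Aim #4 names change scores from before the intervention to "postintervention and 3-month follow-up will be modeled as GLMM similar to above in Aim 3". It does not say which term or combination of terms is the treatment effect at either time. For Aim #3, "covariates can be added to Levels 2 and 3 equations as needed"; the child-level examples are age and baseline anxiety severity.
- **Visits.** The Overview plans a post evaluation after 8 weeks and a "three-month follow-up assessment of the primary (teacher behavior) and secondary (child) outcomes". The student effect size in the Power Analysis is a pre-post one.
- **Referral.** Phase 3 lists the post evaluation, then "Students who need mental health services will be referred to the school counselor or community provider for treatment", then the 3-month visit. The child criteria add that "children identified as needing treatment based on the diagnostic interview (regardless of group) will be referred for services".
- **Service data.** "Students receiving services will also be enrolled; all service use will be documented over the course of the study". The Service Utilization Form "is administered at each assessment to document involvement or changes in psychological/psychiatric services". Aim #4 names no service variable.
- **Order of enrollment.** "Once randomized, teachers will complete their assigned training. Teachers will then identify potentially eligible students from their classes".

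**The concern.** The group-by-time term is the only place in the written equations where group meets time, so an analyst would naturally report it as the treatment effect. What it estimates depends on two things the plan leaves open: whether Aim #4 is fitted to three raw visits or to two change scores, and how timepoint is coded. A straight line through three visits forces a benefit that appears by week 8 and then holds into a steady climb. A benefit that appears and fades can come out as zero.

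The project is meant to produce a training ready for a larger efficacy trial, so readers will look to these student estimates. They need to know which contrast each number is. The 3-month number also needs a note on services, because referral by need takes place before that visit.

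**Working it through.** **Inputs.** From the documents: the Aim #3 equations; post at 8 weeks; follow-up three months later; 20 teachers and 30 students per group; ICC 0.10; alpha .05; student d = 0.92. Assumed: 13 weeks from post to follow-up, and true group differences at baseline, post and follow-up of 0, 0.50, 0.50 SD (maintained) or 0, 0.50, 0 SD (lost).

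**1. The plan's own figure.** The Power Analysis gives 80% power for d = 0.92 with 30 students per group. Take 10 teachers with one student and 10 with two in each arm. Effective n = 10 + 10 × 2/1.10 = 28.2 per arm, and SE = √(2/28.2) = 0.266. A two-sided noncentral t with 38 df gives 92%. About 81% appears only with 20 independent units per arm. The stated figure is therefore conservative. This is separate from the present point, but the SE is used below.

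**2. Three raw visits, numeric time.** Least-squares weights on the three group differences (equal to GLS for complete, balanced visits with equal correlation):

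| Coding | Slope weights (BL, PO, FU) | Fitted difference at post | Fitted difference at follow-up |
|---|---|---|---|
| 0, 1, 2 | −0.5, 0, +0.5 | 1/3, 1/3, 1/3 | −0.167, 0.333, 0.833 |
| weeks 0, 8, 21 | −0.043, −0.007, +0.050 | 0.405, 0.346, 0.249 | −0.154, 0.249, 0.905 |

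- Maintained, coded 0, 1, 2: slope = 0.5 × 0.50 = 0.25; post = (0 + 0.50 + 0.50)/3 = 0.33; follow-up = 0.33 + 0.25 = 0.58. The fit also puts 0.33 − 0.25 = 0.08 at baseline, where the truth is 0.
- Maintained, in weeks: post = 0.50 × (0.346 + 0.249) = 0.30; follow-up = 0.50 × (0.249 + 0.905) = 0.58.
- Lost, coded 0, 1, 2: slope = 0; post = 0.50/3 = 0.17.

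**3. Two change scores.** Two times by two groups give four means, and the model has four fixed effects, so it is saturated. The group-by-time term is follow-up minus post.

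- Coded 0, 1: the group intercept is the post contrast. Maintained gives intercept 0.50 and slope 0; lost gives 0.50 and −0.50.
- Coded 1, 2: the intercept is 2 × post − follow-up. Maintained gives 2 × 0.50 − 0.50 = 0.50; lost gives 2 × 0.50 − 0 = 1.00. The post contrast is then intercept plus slope: 1.00 − 0.50 = 0.50.
- Random effects: two values per student supply three within-teacher moments (two variances, one covariance). A student intercept variance, slope variance, their covariance and a residual variance make four parameters. They cannot all be estimated unless one is fixed, for example the covariance at zero.

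**4. Visit as a category.** Simulation with 400 runs, 20 teachers and 30 students per arm, teacher variance 0.10, visit correlation 0.6 and a student random intercept:

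| Truth at post, follow-up | One slope | Categorical visit |
|---|---|---|
| 0.50, 0.50 | 0.34, 0.59 | 0.49, 0.51 |
| 0.50, 0 | 0.17 at post, slope 0.01 | 0.51, 0.02 |

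The empirical SE of the categorical contrasts in the maintained case was 0.21–0.23.

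**5. Size of the referral component (all inputs assumed).** With a 0.5 SD post difference, the largest gap in the share above any cut-off is 2Φ(0.25) − 1 = 0.197. With 50% uptake and treatment worth 0.5–0.92 SD, the shift is 0.197 × 0.5 × 0.5 = 0.049 to 0.197 × 0.5 × 0.92 = 0.091 SD. If half of those above the cut-off are already served or were referred at baseline, it is 0.025–0.045 SD. The SE is 0.266 for a single visit, or √(4 × 0.4/28.2) = 0.238 for change at correlation 0.6. The largest ratio is 0.091/0.238 = 0.38.

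**6. Cost of a second contrast.** Using the SE in step 1, the minimum detectable d at 80% power is 0.77 at alpha .05, or 0.85 if each contrast is tested at .025. Power at d = 0.92 is 92% or 86%.

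**The case against.** The best reply is that Aim #4 literally names change scores. On that reading the model is saturated and, with post coded 0, the group intercept is exactly the baseline-to-post contrast. A zero group-by-time term beside it correctly says that the effect was maintained. This stands. A reader might infer from the single slope that the plan cannot estimate a post difference at all; the documents do not support that. The 0.33 and 0.58 figures apply only to three raw visits with numeric time, which is how Aim #3 lays out its data. Similarity to Aim #3 also need not mean identity. What remains is that the plan states neither the coding nor the reported term, and that the Aim #3 student random effects do not carry over intact to two values.

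On services, the design is deliberate: the child criteria give a naturalistic rationale, referral applies in both groups, and the data are recorded. A reader might infer that referral invalidates the 3-month comparison. It does not. The intention-to-treat contrast is valid as the effect of training plus need-based referral. The shift in step 5 is small, rests on assumed inputs and has unknown sign: referral by need favors TAT, while more help-seeking by TAPES families would work the other way. The lack of a planned service table is not an error in a pilot.

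A reader might also infer that baseline service use must be adjusted for. It is measured after teachers are randomized and trained, so that choice is debatable.

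Finally, pre-post describes the effect size used in the Power Analysis. Making that contrast the lead is a sensible match, not something the plan declares.

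**Conclusion.** The concern holds as a minor point about the Aim #4 model and its reporting. With three visits and numeric time, a maintained 0.50 SD post difference is fitted as 0.30–0.33 SD, and a lost one gives a zero slope when visits are coded 0, 1, 2. With two change scores nothing is lost in the fixed effects, but the group-by-time term is not the treatment effect, and the student random-slope structure with a free covariance is not identifiable. Naming the contrasts resolves both readings.

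The sizes rest on illustrative true differences and, for the week coding, on the 13-week interval. If the sponsor already intends timepoint as a category, that part needs only to be stated. The service part is supporting description, worth at most about 0.4 of an SE under the assumptions shown. Confidence is medium, because the text leaves the data form and coding open.

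**What to change.** In Aim #4:

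1. Model visit as a category, with a random-effects or covariance structure that the data can support, such as a teacher intercept plus a student intercept or an unstructured visit covariance.
2. Report the baseline-to-post contrast (lead, matching the pre-post effect size in the Power Analysis) and the baseline-to-3-month contrast separately, under intention to treat.
3. As description only, state that the 3-month contrast includes need-based referral. Tabulate new service starts by arm from baseline to post and from post to follow-up, using the Service Utilization Form. Both intervals are needed because the diagnostic interview is also given at baseline, so some referrals may start there. Do not adjust for services started after the student's baseline.
4. Optionally, add a sensitivity analysis adjusting for service use at the student's baseline, shown beside the unadjusted result.

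The cost is one or two degrees of freedom, one table and a second secondary contrast, with the multiplicity price in step 6 if alpha is split. No new visit, form or participant is needed. With about 30 students per arm the table cannot support a formal comparison: power is about 35% for 50% against 30%.

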Sub study: From an economic perspective, anxiety confers a high economic burden on the individual, state and national level. Based on data from 2002, the annual cost of anxiety disorders in the United States is likely to be more than \$100 billion. These cost estimates are 16 years old and an updated examination of the cost of pediatric anxiety disorders is needed. Research has not investigated the potential financial benefit (e.g. school attendance, standardized test scores) or fiscal feasibility of adopting these interventions relative to current practices. Within the United States, it is also uncertain whether the cost burden of pediatric anxiety varies by demographic factors (e.g. minority status, socio-economic status, gender). Each of these cost factors represent sizable gaps in scientific knowledge. In this context, a Pre-K award was submitted to the Connecticut Institute for Clinical and Translational Science in order to fill this important gap in the scientific literature. This sub study will examine the cost of pediatric anxiety and the relative benefit of TAPES compared to usual care (UC). The purpose of this costs and benefits analysis is to provide information to school system administrators and teachers regarding the budgetary consequences of pediatric anxiety and to summarize the cost of achieving potential improvements in school functioning.

Procedures for Summer Months. We will only randomize teachers and enroll students if at least 10 weeks of school remain in the academic year to allow sufficient time to complete baseline evaluation, TAPES implementation and post evaluations.

Randomization. During the RCT, randomization will occur at the teacher level at a 1:1 (20 TAPES: 20 TAT). The randomization plan will be generated prior to the identification of teachers to minimize potential biases. Randomizing teachers to two active training conditions was selected for several reasons. The current design allows for all teachers to receive some training in anxiety identification and reduction—a major recruitment barrier in our previous school-based trials where clinicians or nurses were assigned to a no training control condition and subsequently dropped from the study. In addition, this design allows for an examination of a brief teacher training which represents typical teacher professional development offerings in CT.

Participants and Recruitment

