-Teacher Knowledge Assessment is a 26-item short answer and multiple choice test of anxiety reduction strategies to gauge teachers' prior knowledge and the effectiveness of training. This measure was adapted from an existing knowledge assessment test for school clinicians, which showed an increase in knowledge pre to post-training ([name] et al., 2008).

-*Classroom Observation of Teachers Skills* is a form completed during direct observations of the teacher during normal class activities (e.g., math or reading). The observations are coded by tallying the frequency of specific behaviors that have a positive or negative impact on student anxiety. Using a 5 point Likert scale, observers provide an overall rating of teacher's behavior in both domains.

Usability Measures- The following measures assess whether teachers can understand and learn how to use the skills and whether they can implement the skills effectively and efficiently.

- Teacher Knowledge Assessment (above) will assess ability to learn skills.

- *Classroom Observation of Teachers Skills* (above) will assess use of skills in the classroom. -*Teacher and Child Recruitment Tracker* will be used to record recruitment of teachers/children as well as obstacles to recruitment. Obstacles will be addressed in team meetings and with DT. -*Teacher Time Log* is a form completed by teachers to log the amount of time spent using TAPES/TAT skills with each study student.

Feasibility Measures – The following measures assess whether the training skills can be implemented within an authentic school setting.

-Training Satisfaction and Feedback Questionnaire ([name] et al., 2008, 2011) is a 16-item measure completed anonymously by teachers who rate the helpfulness of training content and format (e.g., role play, videos), overall satisfaction and perceived helpfulness of TAPES/TAT skills for students with anxiety, and their preparedness to conduct conjoint meetings using a 4-point Likert-type scale (1 = not at all helpful to 4 = very helpful). Open-ended questions ask about the most/least helpful aspects of training and suggestions for improvement.

- *TAPES & TAT Satisfaction and Feedback Questionnaires* ([name] et al., 2012) will be adapted for this study from an existing questionnaire and will assess satisfaction and helpfulness of skills used with anxious and in the classroom.

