Data Analytic Plan. Each aim is stated below along with the corresponding data analytic plan. Preliminary analyses and plans for handling missing data are described first.

Preliminary analyses will include: 1) evaluating the psychometric properties of measures, 2) verifying assumptions in analysis of covariance (ANCOVA), general linear model (GLM) and generalized linear mixed model (GLMM), and 3) examining the nature of missing data (e.g., missing at random, MAR). Specifically, we will run descriptive analyses to check for outliers to ensure that distributional assumptions of the planned analyses are appropriate. If not, analogous non-parametric methods will be used. Although all of our primary measures have a favorable psychometric history, we will ensure a satisfactory level of internal consistency for each measure through calculation of Cronbach's alpha.

Missing Data: With respect to missing data, we will follow Bell et al. (2014)'s recommendations which include: 1) make every possible effort to prevent missing data, 2) use the intention-to-treat (ITT) principle and all available data in analyses, and 3) conduct sensitivity analyses that assess the robustness of the results. Thus, our IEs and RAs will review all assessment materials in the presence of teachers, children, and parents to limit the amount of missing data and to help verify the correctness of the data. Because missing data may lead to biased estimation and loss of statistical power if handled inappropriately we will draw upon several approaches if missing data is present (Diggle, Liang, & Zeger, 1994). We will conduct a partial check to determine if the data are missing at random (MAR) by evaluating whether 'missingness' can be explained on the basis of measured variables. Multiple imputation (MI) has been shown to improve upon traditional simple methods for handling missing data (e.g., list-wise deletion, mean substitution; Schafer, 1997). Thus MI ITT results will be compared with other methods such as complete case or maximum likelihood methods in a sensitivity analysis (Soley-Bori, 2013).

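### The 10-week enrolment rule does not secure the 3-month classroom observation in the same school year, and the linear time term in the Aim 3 skills model lets missed or late follow-ups shift the estimate

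*Combined protocol and SAP*

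**What the plan says.** The section Procedures for Summer Months contains the only calendar rule: "We will only randomize teachers and enroll students if at least 10 weeks of school remain in the academic year". It gives its purpose as time for the baseline assessment, the implementation period and the post assessment. Follow-up is not listed.

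Other sections require more:

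- The design overview (Stage three, Phase 3) plans "a post-intervention (after 8 weeks) and a three-month follow-up assessment of the primary (teacher behavior) and secondary (child) outcomes".
- Under Stage 3, Phase 2, teachers implement their assigned training "over 8 weeks from child enrollment". Phase 3 adds: "A 3 month follow-up evaluation to assess sustained use of TAPES/TAT skills will be conducted".
- The skills outcome, listed under Primary Outcomes, is scored from "direct observations of the teacher during normal class activities". Table 1 lists it at baseline, post and follow-up.
- The Aim 3 analysis models the evaluator's rating "for each pair of teacher and anxious student at baseline, post-intervention, and 3-month follow-up". The Level 1 equation has a single coefficient multiplying timepoint. Intercepts and slopes vary by student and by teacher, and group enters both at Level 3.
- The Missing Data section plans to "use the intention-to-treat (ITT) principle and all available data in analyses", checks whether missingness relates to measured variables, and says "MI ITT results will be compared with other methods such as complete case or maximum likelihood methods in a sensitivity analysis".

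No section gives a window for the 3-month visit, or says how an observation made late or with a different class is labelled or analysed.

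**The concern.** The classroom observation needs a class in session. A student can be enrolled within the rule and still reach the 3-month date during the summer break. The observation is then either missed or made in the next school year, probably with a new class (an assumption; the documents do not say).

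This affects the Aim 3 skills result because time is linear. With all three visits and equally spaced time codes, the slope for a teacher-student pair depends only on baseline and follow-up. Without follow-up it depends on baseline and post. What the group-by-time coefficient measures therefore depends partly on when in the year students were enrolled. A late observation is not missing, so under the plan to use all available data it enters as an ordinary 3-month value. If time is instead coded in weeks, a late visit changes the weights.

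**Working it through.** **Calendar.** Inputs: 10 weeks (Procedures for Summer Months); 8 weeks of implementation (Stage 3, Phase 2); 3 months to follow-up (Phase 3), which is 3 × 365.25/12/7 = 13.0 weeks.

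- The plan's own figure: 10 − 8 = 2 weeks remain for the baseline and post assessments. This fits the rule's stated purpose.
- School weeks needed for follow-up: 8 + 13 = 21, or 10 + 13 = 23 with the 2 assessment weeks. The shortfall against 10 is 11 to 13 weeks.
- If the 3 months run from enrolment: 13, or 13 + 2 = 15. Both still exceed 10.

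**Who is affected.** Let L be the school weeks left at enrolment and S the length of summer (assumed 10-16 weeks; not in the documents). School reopens (L − 8) + S weeks after a week-8 post visit, or (L − 10) + S weeks after a week-10 post visit. Class is back by week 13 after post if L ≤ 21 − S or L ≤ 23 − S respectively.

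| Summer S | On time in the new year, post at week 8 | Post at week 10 |
|---|---|---|
| 10 | L = 10-11 | L = 10-13 |
| 11 | L = 10 | L = 10-12 |
| 12 | none | L = 10-11 |
| 13 | none | L = 10 |
| 14-16 | none | none |

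The gap therefore falls mainly between these latest enrolments and L of about 21-23. A visit moved to the new year comes from 2 + 10 = 12 weeks after post (L = 10) to 13 + 16 = 29 weeks (L = 21), against a target of 13.

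The share of participants affected cannot be derived. Stage three spans months 21-34, which is 14 months and so includes a summer. The documents give no enrolment calendar.

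**Effect on the linear slope.** With time codes 0, 1, 2 the least-squares weights are −0.5, 0, +0.5; with codes 0, 1 they are −1, +1. Assume group differences of 0, d and 0.5d at the three visits. A complete pair contributes 0.5 × 0.5d = 0.25d, and a pair without follow-up contributes d.

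Worked case: random intercept only, correlation 0.5, half the follow-ups missed in both arms. The inverse covariance is 2(I − J/4) for three visits and 2(I − J/3) for two, where I is the identity and J the all-ones matrix. Drop the common factor 2 and add the two patterns with equal weight:

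- intercept-intercept: 0.750 + 0.667 = 1.417
- intercept-time: 0.750 + 0.333 = 1.083
- time-time: 2.750 + 0.667 = 3.417
- right-hand sides: 0.375d + 0.333d = 0.708d and 0.875d + 0.667d = 1.542d
- slope = (1.417 × 1.542 − 1.083 × 0.708)d / (1.417 × 3.417 − 1.083²) = 1.417d / 3.667 = 0.386d

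Over a range of cases:

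| Assumed differences (post, follow-up) | 0% missed | 25% | 50% | 75% |
|---|---|---|---|---|
| d, 0.5d; correlation 0.3-0.7 | 0.250d | 0.298-0.305d | 0.378-0.393d | 0.536-0.560d |
| d, d; correlation 0.5 | 0.500d | 0.534d | 0.591d | 0.700d |
| d, 2d (linear growth) | d | d | d | d |

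These rows use a random intercept only, whereas the planned model has random slopes. Adding an assumed slope variance of 0.1 to 0.5 times the intercept-plus-residual variance (correlation 0.5) moves the first row at 50% missed to about 0.43-0.50d.

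**Late visits, time coded in weeks.** Under the first pattern, visits at weeks 0, 8, 21 give weights −0.043, −0.007, +0.050, so −0.007d + 0.050 × 0.5d = 0.018d per week. Visits at weeks 0, 8, 37 (8 + 29) give −0.020, −0.009, +0.029, so 0.005d per week.

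**Categorical time, random intercept, same missing shares.** The post contrast is d and the follow-up contrast 0.5d at every share checked (0-90% missed). The post standard error is unchanged. The follow-up standard error rises 3-4% at 10% missed, 10-11% at 25% and 27-31% at 50%.

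**The case against.** The strongest reply has five parts.

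1. **Some late enrolments are not affected.** A reader might infer that every student enrolled after the 21-23 week mark loses follow-up. The calendar table shows otherwise: with a summer of 10-13 weeks, some of the latest enrolments can be observed on time in the new year. This stands.

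2. **The linear term is the main cause.** The slope blends post and follow-up even with complete data. This stands too. The calendar adds that the blend then varies with enrolment date.

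3. **The size depends on the assumed course of the effect.** With linear growth there is no drift. With d and 1.5d the slope moves only from 0.75d to 0.767d at 25% missed. The protocol's theory of change, in which student improvement reinforces teachers' continued use of skills, makes growth plausible. So the figures are illustrations, not forecasts.

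4. **Missed visits are covered in general terms.** The Missing Data section provides for all available data, multiple imputation and sensitivity analyses. An imputation model with arm-specific visit means could remove the drift from missed visits. The plan does not specify that model, however, and imputation does nothing for late visits that are present in the data.

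5. **A new class does not defeat the purpose.** Follow-up is meant to show sustained use, and the same teacher can still be observed. This stands, and is a reason to label such visits rather than discard them.

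A reader might also infer between-arm bias. The documents do not support that: teachers are randomized 1:1, and nothing shows that enrolment timing or the effect of a class change differs by arm.

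**Conclusion.** The point holds as a limited one. The 10-week rule does what it says, but it does not secure the 3-month classroom observation within the school year. The linear time term then makes the Aim 3 skills coefficient depend on how many follow-ups are missed or late, unless the effect grows linearly. At an assumed 50% missed, 0.25d becomes 0.38-0.39d (random intercept) or about 0.43-0.50d (assumed random slopes) if the effect halves by follow-up. If the effect is fully sustained, 0.5d becomes 0.59d (random intercept).

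These sizes rest on the assumed effect patterns, correlations and slope variances, and on equal missing shares in both arms. The calendar result also rests on reading the 3 months as starting at post, though the shortfall remains if they start at enrolment. The real share affected is unknown and could be small if enrolment is early in the year.

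A direct baseline-to-post contrast is not affected. Nor is the knowledge test, which the Aim 3 text sets at post-training and end of school year. The documents do not support a conclusion that the 10-week rule must be lengthened or that next-year observations are worthless. For a small pilot, the severity is minor to moderate.

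**What to change.** Keep the 10-week rule.

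- In the Aim 3 skills model, enter time as categorical. Report the baseline-to-post and baseline-to-follow-up group contrasts separately. Naming the post contrast as the main skills comparison is optional.
- At each follow-up observation, record the weeks since post (available from visit dates) and whether it is the same or a new class.
- Run one sensitivity analysis limited to on-time, same-class follow-ups, with on-time defined in advance.

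The cost is a wording change, one or two more model parameters (a second time effect and its interaction with group), one form field and one extra analysis. The follow-up contrast will be less precise, as the standard errors above show. No extra visits, recruitment or sample size are needed. Class status is easiest to capture at the visit, so the change is best made before follow-ups begin.
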